# **Prior and Concomitant Medications**

All medications will be characterized according to the start and end date of occurrence related to the vaccination as follows:

- **Pre-vaccination**: start date before the date of injection of study vaccine.
- **Concomitant:** start date before vaccination but continued after vaccination or start date after vaccination. Concomitant medication during the period Day 1- 29 will be labeled if in addition, the start date is on or before the Day 29. If start date and/or stop date is missing or incomplete, medication is considered concomitant unless the information on the stop date is unambiguous before the vaccination date.

Previous vaccination will be categorized by the previous year the latest influenza vaccination was done within the three years prior to the study vaccination. The categories year since last vaccination will be 1 year (if 2020 is the last year), 2 years (if 2019 is the last one) or 3 years (if 2018 is the last one).

# 8.9 Treatment groups

The different treatment groups will be labeled as shown in the table below. The HA antigen content and the MF59 content will be used as co-variates in selected statistical analyses.

Vaccine description HA antigen **MF59** Total injected Sorting volume (mL) Group Vaccine content/ squalene Order strain (µg) content (mg) Α aQIVc 1 and 2 В aQIVc 3 and 6 С aOIVc 6 and 4 D 7 aQIVc 7 and Е aQIVc 9 and 3

 Table 4: Overview of treatment groups

26 Augustus 2021 Final Version 2.0

F	aQIVc 10	and				5
G	aQIVc 11	and				8F
Н	QIVc	15 mcg	15	0	0.5	1

### 8.10 Analysis Software

All analyses will be performed using SAS Software version 9.4 or higher.

# 9. STUDY SUBJECTS

# 9.1 Disposition of Subjects and Withdrawals

All randomized subjects will be accounted for in this study. The numbers and percentages of subjects in each analysis set, study withdrawals, subgroups, and major protocol deviations will be presented. Number of subjects per country and site will be presented by vaccine group and overall for All Enrolled Set.

The time in days (i.e. date of last assessment minus date of vaccination plus 1) the subjects are under observation for safety will be summarized by vaccine group and overall using summary statistics (mean, Standard Deviation, minimum, median, maximum).

All subjects who are randomized will be accounted for in this study. The frequencies and percentages of subjects in each analysis set, study withdrawals, subgroups, and major protocol deviations will also be presented.

# **10. DEMOGRAPHICS AND OTHER BASELINE CHARACTERISTICS**

In general, all tables related to baseline characteristics should include a Total column across vaccine groups.

# **10.1 Demographics**

Age, height, weight, body mass index and Comorbidity Risk Score will be summarized by reporting the mean, standard deviation, median and range, and will be calculated by vaccine group and overall.

In addition, the frequencies of age categories will be reported as 50-64 and  $\ge 65$  years old (age as a randomization stratum) and 50-64, 65-74, and 75-84, and  $\ge 85$  years old. The number and percentages of subjects by sex, ethnic origin, race, previous vaccination history (in past 3 years), country and Comorbidity Risk Score (<50 and  $\ge$ 50) will be presented by vaccine group and overall.

Demographic data will be tabulated for the All Enrolled, FAS, PPS and Safety sets.

The distribution across all stratification factors (age subgroup \* previous vaccination history) will be presented by vaccine group and overall. This table will be presented based on the IRT data and - if different – also for the actual eCRF data.

# **10.2 Medical History**

The numbers and percentages of subjects with medical history will be presented by Medical Dictionary for Regulatory Activities (MedDRA) system organ class (SOC) and preferred term (PT) by vaccine group and overall. Medical history data will be tabulated for the All Enrolled, FAS, PPS and Safety Sets.

# **11. IMMUNOGENICITY ANALYSIS**

The immunogenicity analysis will be descriptive in nature and focus on the estimation of the treatment effects of the seven different aQIVc formulations versus QIVc. All immunogenicity analyses will be evaluated based on the PPS Immunogenicity. In the case that there is >5% difference in the total number of subjects between the PPS and the FAS Immunogenicity, additional analysis based on the FAS Immunogenicity will be conducted.

# 11.1 Blood samples

The frequencies and percentages of subjects with blood draws will be summarized overall and by vaccine group. Data will be tabulated for the All Enrolled Set.

# **11.2 Primary Objectives Analysis**

The primary endpoints in terms of HI antibody response against homologous vaccine strains are defined as:

- Geometric Mean Titer (GMT): Geometric mean of HI antibodies at Day 1 and Day 29.
- Geometric Mean Fold Increase (GMFI): The Geometric mean of the fold increase in serum HI titer post-vaccination (Day 29) compared to pre-vaccination (Day 1).
- Percentages of subjects with HI titers  $\geq$  1:40 at Day 1 and Day 29.
- Percentage of subjects with seroconversion (defined as a ≥4-fold increase in titer post-vaccination in those with pre-vaccination titer above the LLOQ (1:10), or a post-vaccination titer ≥1:40 for subjects with baseline titer below the LLOQ (1:10) for HI antibodies at Day 29).

Note that the HI assay could be replaced by the MN assay in case of a lack of agglutination.

In addition, reverse cumulative distribution plots will be generated to display the distribution of the antibody responses at Day1 and Day 29 for each of the vaccine groups. The x-axis represents the immunogenicity values, and the scale of the axis is logarithmic. The y-axis represents the

percentage of subjects having at least that immunogenicity value. Due to the discrete values of antibody response, the plot will show a step-wise function. The figures begin at 100%, and then descends to the lowest point on the curve, which is the percentage of subjects having an immunogenicity value equal to the highest observed value.

All statistical analyses will be descriptive in nature. No hypothesis testing will be applied.

### **Geometric Mean Titer**

Summary statistics (geometric mean, 95% confidence interval of GMT, minimum, median, maximum) of the titers will be presented by strain, assessment (Day 1 or Day 29) and vaccine group.

The analysis model used for the comparison of the HI (or MN) GMT between each of the seven aQIVc formulations and QIVc will be done using a general linear model on log-transformed (base 10) Day 29 titers as the outcome variable and as covariates: treatment groups as categories (aQIVc1, aQIVc3, aQIVc6, aQIVc7, aQIVc9, aQIVc10, aQIVc11 and QIVc), log-transformed prevaccination titer, age subgroup and previous vaccination history. From this model, adjusted differences in the least square means (on the log scale) will be produced with 95% confidence limits for aQIVc1 versus QIVc, for aQIVc3 versus QIVc, for aQIVc6 versus QIVc, for aQIVc7 versus QIVc, for aQIVc7 versus QIVc, for aQIVc7 versus QIVc, for aQIVc1 versus QIVc. The estimated difference and the confidence limits will be back-transformed to obtain an *adjusted GMT ratio* with 95% confidence limits. Each of the four strains will be analyzed separately.

In addition, a second analysis model will be applied – similar as the model described above but using the amount of antigen and MF-59 dose as factors instead of the treatment groups as category, but with the same covariates age group, previous vaccination history and log-transformed prevaccination titer. Model fit will be assessed, and alternative models may be considered.

Potential interaction between age subgroup and treatment effect will be examined by including an interaction term in the model and present all adjusted GMT ratios with 95% confidence intervals for each age subgroup.

Unadjusted GMT ratio will be based on a simple ANOVA model on the log-transformed titers and the treatment group.

# **Geometric Mean Fold Increase**

Summary statistics (geometric mean, 95% confidence interval of GMT, minimum, median, maximum) of the relative increase in titers will be presented by assessment (Day 29), strain and vaccine group.

The analysis model for the fold increase in titers will be done using the same models as mentioned above on log-transformed (base 10) (Day 29 titers/Day 1 titers) as the outcome variable but excluding the log-transformed pre-vaccination titer.

### Analysis of binary endpoints

The number and proportion of subjects achieving the binary endpoints (seroconversion or HI titer >=1:40) will be summarized by assessment (Day 29), strain and vaccine group.

For each of the influenza vaccine strains and for each of the vaccine groups, summaries will include the associated two-sided 95% confidence intervals according to Clopper-Pearson.

The binary endpoints (i.e. seroconversion or titer  $\geq$ 1:40) will be compared between each aQIVc formulation and QIVc using the Miettinen and Nurminen method without adjustment for the age subgroup. The results will be presented as the difference in the percentage of subjects with 95% confidence intervals.

Additional supportive analyses may be done using generalized linear models with factors for vaccine group, age subgroup, pre-vaccination titer as well as previous vaccination history. Adjusted differences between vaccine groups with 2-sided 95% CI will be calculated based on the model and potential interaction effects will be examined.

# 11.3 Secondary Objectives Analysis

The secondary endpoints in terms of HI antibody response against homologous cell-derived vaccine strains (A/H1N1, A/H3N2, B/Yamagata and B/Victoria) at Day 181, are:

- GMT: Geometric mean of HI antibodies at Day 181;
- GMFI: The Geometric mean of the fold increase in serum HI GMTs post-vaccination (Day 181) compared to pre-vaccination (Day 1);
- Percentages of subjects with HI titers  $\geq$  1:40 on Day 181.

In addition, the humoral immune response in terms of MN antibody response against homologous cell-derived vaccine strains (A/H1N1, A/H3N2, B/Yamagata and B/Victoria) at Days 1, 29 and 181:

- GMT: Geometric mean of MN antibodies at Days 29 and 181;
- GMFI: The Geometric mean of the fold increase in serum MN GMTs post-vaccination (Day 29 and Day 181) compared to pre-vaccination (Day 1);

• Percentages of subjects with seroconversion (defined as ≥ 4-fold increase for subjects with prevaccination MN titers ≥ Lower Limit of Quantitation (LLOQ) or as ≥ 4\*LLOQ for subjects with pre-vaccination MN titer <LLOQ) at Day 29.

The analysis of the secondary immunogenicity endpoints will be conducted in the same way as described for the primary immunogenicity endpoints.

# 11.4 Exploratory Objectives Analysis

Additional analyses may be done on the immunogenicity endpoints as measured on Day 29 by HI or MN assay using cell-derived target viruses or cell-derived heterologous target viruses. Details on this exploratory analysis will be included in a separate statistical analysis plan. The results may be presented in an addendum to the CSR.

# **12. EFFICACY ANALYSIS**

Not applicable.

# 13. SAFETY ANALYSIS

The analysis of safety assessments in this study will include summaries of the following categories of safety data collected for each subject:

- Vaccine exposure;
- Solicited local and systemic adverse events as recorded by the subject;
- Solicited systemic events and injection site pain assessed using the investigator evaluation;
- Unsolicited adverse events;
- Serious AEs, MAAEs, AESIs and AEs leading to withdrawal from study.

# 13.1 Analysis of Extent of Exposure

The frequencies of subjects with vaccinations will be summarized overall and by vaccine group and by age group. Data will be tabulated for the All Exposed Set.

### 13.1.1 Safety Completeness

### **Analysis Solicited Adverse Events**

The safety completeness analysis on solicited adverse events aims to identify subjects who completed the electronic diaries. The analysis will show the number of subjects with valid results by solicited adverse event and day.

Three summaries will be produced:

- 1. The frequencies of subjects who provided any data on the electronic diary cards by vaccine group.
- 2. For each solicited adverse event including analgesic use, the frequencies of subjects with data will be presented by vaccine group and day
- 3. For each solicited adverse event including analgesic use, frequency of the number of days with data on the eDiary by vaccine group.

For the corresponding percentages, the denominator will be the respective number of subjects vaccinated (All Exposed Set).

All analyses will be based on the 'as treated' analysis set.

# 13.2 Solicited Local and Systemic Adverse Events

Each solicited AE is to be assessed by the subject for Day 1 to Day 7 according to a defined severity grading scale; see specifics of the solicited event and grading system below in Table 3.

Table 5 Severity Grading for Solicited Local and Systemic Adverse Events

		Any Event			
Туре	Solicited Event	Grade 1/Mild	Grade 2/Moderate	Grade 3/Severe	
Local Injection site pain No int da		No interference with daily activity	Interferes with daily activity	Prevents daily activity	
	Erythema	25-50 mm	51-100 mm	> 100 mm	
	Induration	25-50 mm	51-100 mm	> 100 mm	
Systemic	Loss of appetite	tite Eating less than Eating less than usual with no effect usual /interfered on normal activity with normal activi		Not eating at all	

		Any Event				
Туре	Solicited Event	Grade 1/Mild	Grade 2/Moderate	Grade 3/Severe		
	Nausea	No interference with daily activity	Interferes with daily activity	Prevents daily activity		
	Fatigue	No interference with daily activity	No interference with daily activityInterferes with daily activity			
	Myalgia	No interference with daily activity		Prevents daily activity		
	Arthralgia	No interference with daily activity	No interference with daily activityInterferes with daily activityNo interference with daily activityInterferes with daily 			
	Headache	No interference with daily activity				
	Chills	No interference with daily activity         Interferes with daily activity		Prevents daily activity		
	Fever	38.0 - 38.4 °C 100.4 – 101.1 °F	38.5 – 38.9 °C 101.2 – 102.0 °F	≥39.0 °C ≥102.1 °F		

Note: presence of an event on a day is defined as grade 1, 2 or 3; absence is defined as non-missing and not present. Erythema and Induration: grading will be derived from the actual measurements in mm; Fever will be derived from the actual temperature.

### Other Indicators of Reactogenicity

The use of analgesics/antipyretics will be captured as "absent" or "present" separately by reason "for treatment" or "for prevention".

The analyses will be based on the solicited safety set and encompass various summaries of the data by vaccine group, overall and by age subgroup.

- 1. Overall summary of subjects with solicited adverse events
- 2. Local Solicited adverse events, maximum event severity by event and time interval (i.e. Day 1-7, Day 1-3, Day 4-7)
- 3. Systemic Solicited adverse events, maximum event severity by event and time interval (i.e. Day 1-7, Day 1-3, Day 4-7)
- 4. Number of days of solicited adverse events, including ongoing AE after Day 7
- 5. Daily reports of subjects with solicited adverse events.
- 6. Day of first onset of solicited adverse events

- 7. Ongoing adverse events at Day 7
- 8. Distribution of maximum temperature
- 9. Other use of analgesics/antipyretics.
- 10. Exploratory analyses to investigate the effect of amount of antigen and MF-59 levels.

For each of the time points or time intervals presented in the summaries, only subjects with at least one valid observation (i.e., any non-missing values) for the solicited adverse events in the interval of interest will be considered. Subjects without valid data will be removed from the denominator to prevent a downward bias (towards zero).

All tables are run by vaccine group, overall and by age subgroup.

# Overall summary of subjects with solicited adverse events.

Any solicited adverse event presence is defined as at least one day recorded a presence of a local or a systemic adverse event. No solicited adverse event is defined as for all days 'No' for all predefined solicited adverse events.

Note that, where applicable, missing values for all days for all events will be excluded from % calculations.

The use of analgesics/antipyretics will be considered in this summary as a separate category under "other", however will be considered as part of reactogenicity.

# Local Solicited adverse events, maximum event severity by event and time interval

The **maximum event severity** will be defined if there is at least one non-missing observation within this time interval. Each subject's data will be aggregated across the time points of the interval and summarized according to the maximal severity observed for each local adverse event, followed by a summary across subjects for each vaccine. Subjects with missing values at each of the requested time points, will be excluded.

The time intervals will be Day 1 to Day 7, Day 1 to Day 3 and Day 4 to Day 7. A summary table will be created with the frequency using only any local solicited AE and severe local solicited events.

# Systemic adverse events, maximum event severity by event and interval

The analysis on the maximum severity of the systemic adverse events will be done along the same methods as for the local adverse events.

# Number of days with solicited adverse events

The number of days with the adverse event is defined irrespective of severity. If a solicited adverse event continues beyond day 7 the period after day 7 is added.

26 Augustus 2021 Final Version 2.0

The frequency distribution of the number of days (including mean and median values) will be provided in a summary table by vaccine and by adverse event. As reference the number of missing days will be presented in a frequency table.

### Daily reports of solicited adverse event

For each of the time points only subjects with at least one non-missing observation for the solicited adverse event in the interval of interest will be considered. Subjects with missing values will be removed from the denominator to prevent a downward bias (towards zero). Data collected will be summarized (frequencies and percentages of subjects) by vaccine group, solicited adverse event, and time point (i.e. by day).

# Time of first onset of solicited adverse events

The **time of first onset** is defined, for each subject, for each solicited adverse event, as the day at which the respective solicited adverse event first occurred. The summary will provide the frequencies and percentages of subjects with first onset of each solicited adverse events by vaccine group and by each time point, as well as mean and median day of onset.

### Adverse events ongoing at Day 7

For each of the solicited adverse events, the number and proportion of subjects in the solicited safety set reported the event ongoing at Day 7 will be summarized.

# Distribution of maximum temperature

Body temperature will be summarized by 0.5 °C increments from 36.0 °C up to  $\geq$ 40 °C by frequency tables.

# Use of analgesics/antipyretics

The use of antipyretics and analgesics will be summarized as "other" by type of use (prophylactic versus treatment) as the number and percentage of subjects reporting use.

# Exploratory analyses to investigate the effect of amount of antigen and MF-59 levels.

A logistic regression analysis will be applied with the binary response (presence of solicited adverse reaction or no reaction), to explore the relation with antigen and MF59 levels as factors as well as with age and previous vaccination history. This model will be applied for both reported solicited local or systemic adverse events (AEs) for 7 days following vaccination and reported severe solicited local or systemic AEs for 7 days following vaccination (Day 1 through Day 7).

#### 13.3 Investigator assessment of Solicited Adverse Events

The solicited systemic events and injection site pain will also be assessed by the investigator. For each subject, the investigator will assess if the subject's solicited symptoms are consistent with the data reported in the e-diary. If no, the investigator will record the evaluation of the solicited systemic events and injection site pain for consistency with eDiary and if not presence or absence, and if present the maximum severity and start and stop date. If yes, the subject's eDiary data will be mapped to the investigator's assessment.

A frequency table will be presented on the consistency assessment of the investigator (yes/no) by vaccine group and total.

Furthermore, the overall occurrence during Day 1 to 7 after vaccination for each of the solicited systemic events and injection pain based on the investigator assessment will be tabulated by vaccine group for total and by age group. The same summaries will be presented by the maximum severity including the occurrence of severe events according to the investigator. All subjects for which an investigator assessment has been done will be included in these analyses.

#### 13.4 Unsolicited Adverse Events

This analysis applies to all AE's occurring during the study, judged either as probably related, possibly related, or not related to vaccination by the investigator, recorded in the AE eCRF.

The original verbatim terms used by investigators to identify adverse events in the eCRFs will be mapped to preferred terms using the MedDRA dictionary.

The adverse events will then be grouped by MedDRA preferred terms into frequency tables according to system organ class. All reported AEs, as well as AEs judged by the investigator as at least possibly related to study vaccine, will be summarized according to system organ class and the preferred term within system organ class. These summaries will be presented by vaccination group. When an AE occurs more than once for a subject, the maximum severity and strongest relationship to the vaccine group will be counted.

The assignment to safety follow-up time intervals will be done by day of onset and not by days ongoing/persisting.

26 Augustus 2021 Final Version 2.0

The summaries will be presented by period of onset (Day 1 to Day 29, Day 30 to end of study or Day 1 to end of study). An overview summary will be created by time -period with number and % of subjects with the following categories:

- AE
- AE by maximum severity
- Related (i.e. at least possible) AE
- SAEs
- Related SAEs
- AESIs
- MAAEs
- AEs leading to withdrawal from study
- Deaths.

The following summaries will be produced by SOC and Preferred Term and by time-period (Day 1 to Day 29, Day 30 to end of study or Day 1 to end of study):

- AEs
- AEs by maximum severity
- AEs that are possibly or probably related to the vaccine
- SAEs
- SAEs that are possibly or probably related to the vaccine
- AESIs
- MAAEs
- AEs leading to withdrawal
- Deaths.

Data listings of all adverse events will be provided by subject. In addition, adverse events in the categories above will be provided as listed data.

All tables will be produced overall and by age subgroup.

Print Date (Local): 26-Aug-2021 16:31:00

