#### Subject eDiary

Electronic Diaries (eDiaries), hereafter referred to as Subject eDiaries, will be the primary source document for solicited local and systemic AEs (including body temperature measurements). These AEs will be recorded in the eDiary by the subject, starting after the initial 30-minute post-vaccination period at the clinic, and continuing for 7 consecutive days (or longer if the events are not resolved). Refer to the user's manual for further details.

The Investigator or delegated, qualified healthcare staff should review the Subject's eDiary data and monitor the Subject's eDiary status for compliance on an ongoing basis during eDiary use (Day 1 through Day 7) or longer if events are not resolved.

- 1. The Subject eDiary will be designed in such a way as to prevent any blank, incomplete or biologically implausible entries during eDiary completion. Subjects will be instructed to fully complete the Subject eDiary each day, as per the instructions provided.
- 2. Before or just after vaccination, site staff must ensure that each subject's eDiary is prepared for data capture in the ensuing post-vaccination period.
- 3. Any new safety information reported during the site visit cannot be entered into the Subject eDiary. Such information must be described in the source notes as a verbally-reported event. Any unsolicited adverse reaction reported in this fashion must be described as an unsolicited reaction and therefore entered on the AE page of the eCRF.
- 4. For any solicited systemic reactions or injection site pain where the investigator evaluation in the Day 7 Safety Follow-up call differs from the eDiary data (eg. presence/absence or severity), the maximum severity and start- and stop dates will be reported in the 'Safety Phone Call Day 7 eCRF' page.

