#### **Observation Period**

After vaccination, the subject will be observed for at least 30 minutes including observation for immediate post-vaccination AEs (unsolicited). All safety data collected during this time will be recorded in the subject's source document and in the Adverse Event eCRF.

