### **Other Indicators of Reactogenicity**

The use of analgesics/antipyretics will be captured as "absent" or "present" separately by reason "for treatment" or "for prevention".

The study staff must review the data entered into the Subject eDiary as described in Section 3.6.2, Tools Used for Data Collection and Section 5.4, Post-vaccination Visits.

Note: Any solicited AE that meets any of the following criteria must be entered into subjects' source document (see Section 9.1, Source Documentation) and also as an AE on the AE eCRF:

- Solicited local or systemic AE that leads to an unscheduled visit to a healthcare provider (MAAE, see Section 7.1.3, Evaluation of Adverse Events).
- Solicited local or systemic AE leading to the subject withdrawing from the study or the subject being withdrawn from the study by the investigator (AE leading to withdrawal, see Section 7.1.3, Evaluation of Adverse Events).
- Solicited local or systemic AE that otherwise meets the definition of a serious AE (see Section 7.1.4, Serious Adverse Events).

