#### 7.1.2 Unsolicited Adverse Events

An unsolicited AE is an AE that was not solicited using a Subject eDiary and that was spontaneously communicated by a subject who was vaccinated with one of the study vaccines.

Potential unsolicited AEs may be medically attended (defined as symptoms or illnesses requiring hospitalization, or emergency room visit, or visit to/by a qualified healthcare professional), or were of concern to the subject. In case of such events, subjects will be instructed to contact the site as soon as possible to report the event(s). The detailed information about the reported unsolicited AEs will be collected by the qualified site personnel during the interview and will be documented in the subject's records.

The period of observation for AEs extends from the time the subject has received the study vaccine until the subject either completes the specified safety follow-up period (Day 181) or at early study termination.

All unsolicited AEs that start during the treatment period (Day 1 to Day 29) will be recorded in the eCRF. During the follow-up (Day 30 to Day 181), unsolicited AEs that meet any reporting criterion (an SAE, AESI, AE leading to withdrawal or a MAAE) are to be recorded in the eCRF.

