#### 8.4.3.1.3 Analysis of Unsolicited Adverse Events

This analysis applies to all AEs occurring during the study, judged either as probably related, possibly related, or not related to vaccination by the investigator, recorded in the AE eCRF, with a start date on or after the date of vaccination. The original verbatim terms used by

investigators to identify adverse events in the eCRFs will be mapped to preferred terms using the MedDRA dictionary.

The adverse events will then be grouped by MedDRA preferred terms into frequency tables according to system organ class. All reported AEs, as well as AEs judged by the investigator as at least possibly related to study vaccine, will be summarized according to system organ class and the preferred term within system organ class. These summaries will be presented by the vaccination group and by the interval of study observation (Day 1 to Day 29, Day 30 to end of study). When an AE occurs more than once for a subject, the maximal severity and strongest relationship to the vaccine group will be counted.

Separate summaries will be produced for the following categories

- AEs
- SAEs
- AEs that are possibly or probably related to the vaccine
- SAEs that are possibly or probably related to the vaccine
- AESIs
- MAAEs
- AEs leading to withdrawal

Data listings of all adverse events will be provided by subject.

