### **Unsolicited Adverse Events**

All adverse events will be characterized according to the date of occurrence related to the vaccination. If the start date is before the date of injection of study vaccine or indicated as on injection day but before injection, these events will not be considered as unsolicited adverse events and mapped to the medical history.

Note: If an adverse event start date is missing or unknown and no indication is provided on the timing, the adverse event will be considered as unsolicited adverse event.

When start and/or end dates of an adverse event are only partially known, adverse events will be categorized as unsolicited adverse event unless the partial end date is before the vaccination date.

All unsolicited adverse events emergent will be categorized as occurring during the treatment period of 28 days following vaccination (period Day 1 to Day 29) based on the start date. If start date is missing, events will be counted as yes during the period of 28 days following vaccination.

26 Augustus 2021 Final Version 2.0

The **maximum event severity** is the greatest severity associated with a preferred term (PT) for a reported adverse event according to the following order: Mild < Moderate < Severe.

**Vaccination-related Adverse Events** are those for which the cause has been evaluated by the investigator, and recorded as possibly related, probably related or unknown/ missing.

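### Solicited reactions that must also be entered on the AE eCRF are counted again as unsolicited AEs, because the SAP has no rule to separate them

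*SAP*

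**What the plan says.** **Definition.** Protocol 7.1.2: "An unsolicited AE is an AE that was not solicited using a Subject eDiary". Protocol 8.1.1.2 lists solicited AEs (Day 1-7, from the eDiary) and unsolicited AEs (Day 1-29) as separate primary safety endpoints.

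**Analysis scope.** SAP 13.4 opens: "This analysis applies to all AE's occurring during the study". It sets its scope by the form on which an event is written, whatever the causality judgement, down to events judged "not related to vaccination by the investigator, recorded in the AE eCRF". Protocol 8.4.3.1.3 does the same, with one limit: events "recorded in the AE eCRF, with a start date on or after the date of vaccination". The derivation rule in SAP 8.8 is also a date rule: "All adverse events will be characterized according to the date of occurrence related to the vaccination". None of these looks at the event term or asks whether the event was already solicited.

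**Two routes onto the AE eCRF for solicited-type events.**
- Protocol 7.1.1 (Other Indicators of Reactogenicity) lists solicited events that must be entered on the AE eCRF as well. The first is a "Solicited local or systemic AE that leads to an unscheduled visit to a healthcare provider"; the other two are those that lead to withdrawal and those that are serious.
- Protocol 5.3 says that after vaccination "the subject will be observed for at least 30 minutes including observation for immediate post-vaccination AEs (unsolicited" and sends these findings to the AE eCRF. Under Protocol 3.6.2, eDiary entries run for 7 days, "starting after the initial 30-minute post-vaccination period at the clinic".

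**The concern.** The unsolicited tables are meant to show what the eDiary did not ask about. Under the stated rules they will also contain some of what it did ask about. A Grade 2 arm reaction that takes the subject to a doctor is in the eDiary, so it counts as solicited. It is then copied to the AE eCRF, so it counts as an unsolicited AE too.

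The related-AE rows are the most exposed. Protocol 7.1.3 defines probably related by reasonable timing and no alternative explanation, which fits most injection reactions. SAP 8.8 also counts an unknown or missing causality as related.

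At stake is the safety side of the choice of formulation for Phase 3. The tables are descriptive and each arm has about 100 subjects, so no test would discount a difference of a few subjects between arms.

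**Working it through.** The plan states no figure on this point, so there is none to reproduce. The check has two parts.

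**1. Trace each kind of event to its tables**

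| Event | eDiary | AE eCRF | Solicited endpoint | Unsolicited Day 1-29 tables |
|---|---|---|---|---|
| Solicited AE, not medically attended, not serious, no withdrawal | yes | no | counted | not counted |
| Solicited AE that is medically attended, serious or leads to withdrawal (Protocol 7.1.1) | yes | yes, in addition | counted | counted again |
| Solicited-type reaction in the first 30 minutes that persists and is entered on Day 1 | yes | yes | counted | counted |
| Solicited-type reaction in the first 30 minutes, never entered in the eDiary | no | yes | absent | counted |

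The second row is the clear contradiction: the event was solicited by eDiary, yet it is analysed as unsolicited. In the third and fourth rows the SAP follows the label in Protocol 5.3.

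**2. Bound the size**

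The documents give no background unsolicited AE rate and no rate of immediate or medically attended solicited reactions, overall or by arm. All inputs below are assumptions.

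Let u be the true share of subjects with an unsolicited AE, the same in both arms. Let s be the share with a solicited-type record on the AE eCRF. If the two are independent:

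- observed rate = u + (1 - u)s
- spurious difference = (1 - u)(s in the aQIVc arm - s in the QIVc arm)

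| u | s, QIVc vs aQIVc | Observed rates | Spurious difference (points) |
|---|---|---|---|
| 10% | 1% vs 2% | 10.9% vs 11.8% | 0.9 |
| 10% | 1% vs 5% | 10.9% vs 14.5% | 3.6 |
| 10% | 2% vs 10% | 11.8% vs 19.0% | 7.2 |
| 20% | 1% vs 2% | 20.8% vs 21.6% | 0.8 |
| 20% | 1% vs 5% | 20.8% vs 24.0% | 3.2 |
| 20% | 2% vs 10% | 21.6% vs 28.0% | 6.4 |
| 30% | 1% vs 2% | 30.7% vs 31.4% | 0.7 |
| 30% | 1% vs 5% | 30.7% vs 33.5% | 2.8 |
| 30% | 2% vs 10% | 31.4% vs 37.0% | 5.6 |

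With about 100 subjects per arm, this runs from under one subject to about seven. If s is equal across arms, the difference is zero and each arm is raised by (1 - u)s. For s = 2% that is 0.70 × 2 = 1.4 to 0.90 × 2 = 1.8 points.

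For the solicited endpoint, let q be the share with an immediate reaction that never reaches the eDiary, and p the share with some other eDiary event. The loss from the any-solicited-AE rate is q(1 - p). With q = 1-5% and p = 30-70%, it lies between 0.01 × 0.30 = 0.3 points and 0.05 × 0.70 = 3.5 points. The Protocol 7.1.1 route loses nothing, because the eDiary record stays.

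**The case against.** The case on the other side has several parts.

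- **Both solicited and unsolicited endpoints are wrong.** A reader might infer this. The documents do not support it for the Protocol 7.1.1 route: the eCRF entry is additional, and the solicited endpoint rests on the eDiary alone, so it is unchanged. These events also belong on the AE eCRF, because SAEs, MAAEs and AEs leading to withdrawal form a primary safety endpoint of their own.
- **The 30-minute events follow the protocol.** Protocol 5.3 labels them unsolicited, and the eDiary is not yet running. This stands: it is a convention of the protocol, not an error in the SAP. A reaction that persists can still be entered on Day 1, and SAP 13.3 tabulates the investigator's own assessment of systemic events and injection site pain.
- **The inflation rises with MF59.** A reader might infer this too. Protocol 1.3 reports more solicited AEs at the highest MF59 dosages in the earlier aTIV study. It also reports no apparent trend in unsolicited AEs there, and mostly mild to moderate reactions. It gives no rates by arm and does not say how that study classified such records. The gradient is plausible but not shown.
- **The overlap would be visible.** Tables are by preferred term, MAAEs and SAEs have their own rows, and SAP 13.5 adds a combined summary. This helps only in part. A preferred-term row does not show which records are eDiary copies, and the any-AE and related-AE rows cannot be corrected from it. The combined summary does not change the separate tables. The subject listings that would settle it are not produced at the Day 29 analysis (Protocol 8.6, SAP 14), which is the one meant to inform Phase 3.
- **The effect may be trivial.** At 1% versus 2% it is below one subject per arm. That is fair, and nothing in the documents excludes it.

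**Conclusion.** The gap is real and follows from the text alone. Solicited AEs that are medically attended, serious or lead to withdrawal are counted a second time in the Day 1-29 unsolicited AE and related-AE tables, against the definition in Protocol 7.1.2. Solicited-type reactions in the first 30 minutes enter the same tables by the protocol's own label, and those never entered in the eDiary are missing from the solicited endpoint.

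The size cannot be fixed from the documents. The range of about 0.7 to 7.2 points rests on assumed shares, an assumed background rate of 10-30% and independence of the two kinds of event. If the affected subjects tend to have a true unsolicited AE as well, the any-AE row moves less. The low end may be the realistic one. The documents establish neither a dose-related bias nor damage to the eDiary-based solicited endpoint from the copied events. The change is worth making because the rule gives a wrong count and is cheap to correct.

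**What to change.** In SAP 8.8 and 13.4, before unblinding:

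1. Flag each AE eCRF record that matches one of the 11 solicited terms in Protocol Table 7-1 and has onset on Day 1-7. Identify separately those that began in the 30-minute observation.
2. Exclude the records that are copies of eDiary-solicited events under Protocol 7.1.1 from the main unsolicited AE and related-AE summaries.
3. Show those summaries with and without all flagged records, with the 30-minute events identified.
4. Keep every flagged record in the SAE, MAAE and AE-leading-to-withdrawal summaries. Add a footnote that these rows are not subsets of the unsolicited AE row.
5. Leave the primary solicited endpoint eDiary-only and do not move AE eCRF records into it. A transfer would conflict with Protocol 8.1.1.2 and the Solicited Safety Set in SAP 7.5. It would also conflict with the millimetre grading of erythema and induration, since an AE eCRF term does not supply that measurement.

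Because Protocol 8.4.3.1.3 has the same scope as SAP 13.4, list the change in SAP 16.

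Cost: SAP wording, a preferred-term list, a programming flag and one extra set of tables. SAP 13.5 already plans MedDRA coding of solicited events, so much of the list should exist. No new data are needed. Matching preferred terms takes some judgement, which is why it should be settled before unblinding.
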